Study D4190C00006: The safety profile of durvalumab and tremelimumab combination therapy in the 102 subjects with advanced NSCLC in Study D4190C00006 is generally consistent with that observed across 177 subjects treated with durvalumab and tremelimumab combination therapy (not including subjects treated with blinded investigational product). As of 15Apr2015, 95 of 102 subjects (93.1%) reported at least 1 AE. All subjects in the tremelimumab 3 and 10 mg/kg dose cohorts experienced AEs; subjects in the durvalumab 20 mg/kg and tremelimumab 1 mg/kg Q4W cohort experienced the lowest AE rate (77.8%). Treatment-related AEs were reported in 74 of 102 subjects (72.6%), with events occurring in > 10% of subjects being diarrhea (27.5%), fatigue (22.5%), increased amylase and pruritus (14.7% each), rash (12.7%), colitis (11.8%), and increased lipase (10.8%). Treatment-related \geq Grade 3 AEs reported in \geq 5% of subjects were colitis (8.8%), diarrhea (7.8%), and increased lipase (5.9%). Five subjects reported treatment-related Grade 4 events (sepsis, increased ALT, and increased AST in 1 subject; increased amylase in 2 subjects; myasthenia gravis in 1 subject; and pericardial effusion in 1 subject) and 2 subjects had treatment-related Grade 5 events (polymyositis and an uncoded event of neuromuscular disorder [VT]); the Grade 4 event of myasthenia gravis and Grade 5 polymyositis occurred in 1 subject. There were 2 subjects (both in the MEDI4736 20 mg/kg + tremelimumab 3 mg/kg Q4W cohort) with dose-limiting toxicities (DLTs): 1 subject with Grade 3 increased AST, and 1 subject with Grade 3 increased amylase and Grade 4 increased lipase. Fifty-six subjects (54.9%) reported SAEs, with events occurring in > 5% of subjects being colitis (9.8%) and diarrhea (7.8%). Thirty-six subjects (35.3%) experienced treatment-related SAEs. Twenty-seven subjects (26.5%) permanently discontinued treatment due to AEs. Treatment-related AEs resulting in discontinuation in \geq 2 subjects were colitis (7 subjects), pneumonitis (5 subjects), diarrhea (3 subjects), and increased AST (2 subjects). Additional safety results from this study are presented in the durvalumab and tremelimumab IBs.

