Radiologic tumor assessment will be repeated every 8 weeks ± 7 days for the first 48 weeks and then every 12 weeks ± 7 days until PD. For patients who remain progression free 2 years post completion of protocol directed treatment, every 6 months ± 1 month. Patients who discontinue treatment for reasons other than progression may continue efficacy assessments until progression is demonstrated. Patients who demonstrate radiologic progression by RECIST criteria may be considered for continued therapy (but not primary efficacy analysis) if they are deemed to be clinically benefiting, according to predetermined permitted criteria (section 12.4). Safety will be evaluated in this study through the monitoring of all serious and non-serious AEs and irAEs, graded according to the current version of the National Cancer Institute Common Terminology Criteria for Adverse Events (CTC v.4.03).

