12.4 Response Criteria

Evaluation of Target Lesions

Complete Response (CR): Disappearance of all target lesions. Any pathological lymph nodes (whether target or non-target) must have reduction in short axis to < 10 mm.

Partial Response (PR): At least a 30% decrease in the sum of the diameters of target lesions, taking as reference the baseline sum diameters.

Progressive Disease (PD): At least a 20% increase in the sum of the diameters of target lesions, taking as reference the smallest sum on study (this includes the baseline sum if that is the smallest on study). In addition to the relative increase of 20%, the sum must also demonstrate an absolute increase of at least 5 mm. (Note: the appearance of one or more new lesions is also considered progressions).

Stable Disease (SD): Neither sufficient shrinkage to qualify for PR nor sufficient increase to qualify for PD, taking as reference the smallest sum diameters while on study.

Evaluation of Non-Target Lesions

Complete Response (CR): Disappearance of all non-target lesions and normalization of tumor marker level. All lymph nodes must be non-pathological in size (< 10 mm short axis). Note: If CA125 is initially above the upper normal limit, it must normalize for a patient to be considered in complete clinical response.

Non-CR/Non-PD: Persistence of one or more non-target lesion(s) and/or maintenance of CA125 level above the normal limits.

Date:

Progressive Disease (PD): Appearance of one or more new lesions and/or unequivocal progression of existing non-target lesions. Unequivocal progression should not normally trump target lesion status. It must be representative of overall disease status change, not a single lesion increase.

Although a clear progression of “non-target” lesions only is exceptional, the opinion of the treating physician should prevail in such circumstances, and the progression status should be confirmed at a later time by the review panel (or Principal Investigator).

Evaluation of Best Overall Response

The best overall response is the best response recorded from the start of the treatment until disease progression/recurrence (taking as reference for progressive disease the smallest measurements recorded since the treatment started). The patient's best response assignment will depend on the achievement of both measurement and confirmation criteria.

For Patients with Measurable Disease (i.e., Target Disease)

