Progression-Free Survival (PFS) is defined as the duration of time from start of treatment to time of recurrence, progression, or death, whichever occurs first.

Survival

Survival is defined as the duration of time from start of treatment to time of death or the date of last contact whichever occurs first.

Permitted Deviations from RECIST

The study's efficacy objectives will be evaluated according to the standard, unmodified RECIST v1.1 criteria described in section 12.3, and that, within the context of this protocol, the only purpose of the modifications to the criteria is to allow certain patients to continue the study treatment despite meeting RECIST criteria for progression of disease.

The response to immunotherapy may differ from the typical responses observed with cytotoxic chemotherapy including the following ([name] et al 2009, Nishino et al 2013):

- Response to immunotherapy may be delayed
- Response to immunotherapy may occur after POD by conventional criteria
- The appearance of new lesions may not represent POD with immunotherapy
- SD while on immunotherapy may be durable and represent clinical benefit.

Date:

As long as they are receiving treatment on protocol, patients will be permitted to continue study treatment after RECIST v 1.1 criteria for POD are met if they meet all of the following criteria:

- Absence of symptoms and signs indicating unequivocal progression of disease
- No decline in ECOG performance status
- Absence of tumor growth at critical anatomical sites (e.g., leptomeningeal disease) that cannot be managed by protocol-allowed medical interventions
- Patients for whom approved therapies exist must provide verbal consent to acknowledge deferring these treatment options in favor of continuing study treatment at the time of initial apparent progression

Patients with radiographic disease progression at the at subsequent tumor assessment may be considered for continued study treatment at the discretion of the investigator if they continue to meet the criteria above and have evidence of clinical benefit.

Modification of RECIST as described may discourage the early discontinuation of durvalumab and tremelimumab and provide a more complete evaluation of its anti-tumor activity than would be seen with conventional response criteria. Nonetheless, the efficacy analysis will be conducted by programmatically deriving each efficacy endpoint based on RECIST v 1.1 criteria.

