13.0 CRITERIA FOR REMOVAL FROM STUDY

Patients may withdraw from the study at any time. Any patient who withdraws will be encouraged to return to the study center for a treatment completion visit. Patients who discontinue early should return within 30 days following the final dose of study treatment. The primary reason for discontinuation must be recorded in the medical record.

Permanent discontinuation of treatment with Durvalumab and Tremelimumab

An individual subject will not receive any further investigational product if any of the following occur in the subject in question:

- Disease progression, per investigator assessment
- Intolerable toxicity of study drugs
- Withdrawal of consent or lost to follow-up
- Adverse event that, in the opinion of the investigator or the sponsor, contraindicates further dosing
- Subject is determined to have met one or more of the exclusion criteria for study participation at study entry and continuing investigational therapy might constitute a safety risk
- Pregnancy or intent to become pregnant
- Grade \geq 3 infusion reaction

Date:

- Initiation of alternative anticancer therapy including another investigational agent

Other reasons for patient discontinuation may include, but are not limited to, the following:

- Change in patient eligibility
- Non-compliance
- Patient decision
- If treatment is delayed for more than 28 consecutive days
- Withdrawal of consent
- If consent is withdrawn, the subject will not receive any further investigational product or further study observation.
- The investigator has the right to discontinue a patient from the study for any medical condition that the investigator determines may jeopardize the patient's safety if he or she continues in the study; for reasons of noncompliance (e.g., missed doses, visits); or if the investigator determines it is in the best interest of the patient.

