- Progression free survival (PFS), defined as the duration of time from start of treatment to time of recurrence, progression, or death due to any cause, whichever occurs first. Patients will be censored at last follow up date. The Kaplan Meier estimate of median PFS will be reported as well as the PFS rate at 24 weeks (+/- 1 week).
- Duration of response (DOR), defined as the time from which measurement criteria are met for CR or PR (whichever status is recorded first using RECIST) until the first date of documented

Date:

disease progression, will be estimated using the Kaplan Meier method. Patients without documented progression will be censored at last follow up.

- The rate of response using immune response criteria (refer to irRECIST description in section 12.3, which defines responders and non responders) and the 90% confidence interval will be estimated using exact binomial proportions.
- Adverse events by the current version of Common Terminology Criteria for Adverse Events version 4 (CTCAE v4.03) will be tabulated in order to assess the safety profile and tolerability therapy in treated patients.

Safety Analysis

The frequency and severity of observed adverse effects will be evaluated. The rates of irAE, SAE, therapy completion rate, and protocol completion will also be reported.

Safety will be measured by the frequency of grade 3 or 4 treatment-related clinically significant toxicities (NCI Common Terminology Criteria for Adverse Events version 3.0), aside from Grade 3 or 4 hematologic or laboratory abnormalities, unless they are deemed unexpected or clinically significant.

Frequencies of toxicities will be tabulated. The grade 3 or 4 treatment-related non-hematologic/non-laboratory toxicity will be estimated at the end of the trial along with the 95% confidence interval. With 40 patients per arm, these rates can be estimated within $\pm 16\%$.

Methods of Efficacy Analysis

Efficacy Variables

The intent of this protocol is to assess checkpoint inhibitors for activity in patients with carcinomas advanced, recurrent endometrial carcinomas and carcinosarcomas.

The principal parameters employed to evaluate the efficacy of the two arms are:

- The rate of ORR and duration of overall objective response (ORR = CR + PR).
- Progression-free survival rate at 24 weeks for all patients evaluable for this endpoint.
- Clinical Benefit Rate (CBR) will be defined as ORR + Stable Disease (SD) rate by 24 weeks.

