Tumour assessment (CT or MRI)	For subjects who achieve disease control following 12 months of treatment , tumour assessments should be performed every 12 weeks relative to the date of first infusion thereafter until PD. For subjects who discontinue Durvalumab due to toxicity (or symptomatic deterioration) , tumour assessments should be performed relative to the date of first infusion as follows: every 8 weeks for the first 48 weeks, then every 12 weeks until PD. For patients who remain progression free 2 years post completion of protocol directed treatment, every 6 months +/- 1 month. Upon PD, scans should be conducted according to local standard clinical practice and submitted for central review until a new treatment is started (these scans are optional).							

^a T4 will only be measured if TSH is abnormal. They should also be measured if there is clinical suspicion of an adverse event related to the endocrine system.

Date:

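### Starting another systemic anticancer drug before progression has no stated effect on response, PFS or duration of response, so that drug's effect would count toward an arm's decision rules

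*Combined protocol and SAP*

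**What the plan says.** - **Response window.** Section 12.4: "The best overall response is the best response recorded from the start of the treatment until disease progression/recurrence". Neither the end of study drug nor the start of another drug closes it.
- **PFS.** Section 12.4: "Progression-Free Survival (PFS) is defined as the duration of time from start of treatment to time of recurrence, progression, or death, whichever occurs first". Section 14.0 adds: "Patients will be censored at last follow up date".
- **Duration of response.** Section 14.0: "Patients without documented progression will be censored at last follow up".
- **Assessment after stopping study drug.** Section 4.3: "Patients who discontinue treatment for reasons other than progression may continue efficacy assessments until progression is demonstrated". For patients who stop for toxicity or symptomatic deterioration, Appendix A schedules scans every 8 and later every 12 weeks until progression.
- **New therapy.** Section 13.0 lists "Initiation of alternative anticancer therapy including another investigational agent" among the reasons for giving no further study drug. It says nothing about endpoints. The one scan rule that mentions new treatment concerns optional scans after progression (Appendix A): "Upon PD, scans should be conducted according to local standard clinical practice and submitted for central review until a new treatment is started".
- **Failure rules.** Section 14.0 counts a patient as a failure for the ≥10 rule if she has not progressed but has not been followed for 6 months. In a sensitivity analysis, patients with no post-baseline assessment are non-responders and PFS events.

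**The concern.** Take a patient who stops for toxicity at week 6, starts chemotherapy at week 10, has a partial response at week 16 and has not progressed at week 24. Under the written definitions she is a responder and is progression-free for her arm, although both may be due to the chemotherapy.

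The decision rules are small counts, and if both arms reach 7 responders the one with the higher ORR wins (Section 14.0). One patient can therefore change a conclusion. Elsewhere the plan does treat the switch as a boundary: SAE reporting may end when alternative anticancer therapy starts (Section 17.2.1.4), and retreatment is barred after intervening systemic therapy (Section 9.1). Section 14.0 also sets overall survival aside because of later treatments. The same contamination is left open for both primary endpoints.

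The point concerns non-protocol systemic therapy after study drug has stopped, not local palliative treatment of a lesion.

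**Working it through.** **1. The plan's own figures (Section 14.0).**

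ORR pass probability at true rate p: sum over x ≥ 3 of P(Bin(27, p) = x) × P(Bin(13, p) ≥ 7 − x).
- p = 0.10 gives 0.0977; p = 0.25 gives 0.9001. Stated: 10% and 90%.

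24-week PFS: P(Bin(40, p) ≥ 10).
- p = 0.15 gives 0.0672; p = 0.35 gives 0.9356. Stated: 7% and 94%.

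The design is correct as stated. The question is what is counted.

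**2. One wrongly credited patient.** No switching or discontinuation rate is needed.
- ORR: one non-responder credited after stage 1 means that 6 true responders reach the bar of 7. With ≥3/27 then ≥6/40 at p = 0.10, the false-positive rate is 0.196, against 0.098.
- PFS: one credited patient means that 9 reach the bar of 10. P(Bin(40, 0.15) ≥ 9) = 0.135, against 0.067.

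**3. How often it might happen: illustration only.**

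ORR: p = 0.10 + 0.90 × d × s × q, where
- d is the share of the arm stopping for adverse events. Section 3.0 gives 26.5% for the combination (27/102: "Twenty-seven subjects (26.5%) permanently discontinued treatment due to AEs") and 7.6% for durvalumab alone (23/303), both in lung cancer studies. I add 10% as an assumed intermediate value.
- s is the share of those who start new therapy before progression. It is assumed to be 20–50%; the documents give no figure.
- q is the response rate on the new drug: 0–25%, the full range of the Section 14.0 table of agents (etoposide 0%, doxorubicin 9.3%, ixabepilone 12%, bevacizumab 17%, paclitaxel 25%).

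| d | Highest p (s = 0.5, q = 0.25) | ORR false-positive rate, q from 0 to 25% |
|---|---|---|
| 26.5% | 0.10 + 0.90 × 0.265 × 0.5 × 0.25 = 0.1298 | 9.8% to 25% |
| 10% (assumed) | 0.10 + 0.90 × 0.10 × 0.5 × 0.25 = 0.1113 | 9.8% to 14.8% |
| 7.6% | 0.10 + 0.90 × 0.076 × 0.5 × 0.25 = 0.1086 | 9.8% to 13.5% |

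PFS: p = 0.15 + 0.85 × d × s × q, with q from 8.0% to 41.5% (24-week PFS in the same table).
- d = 26.5%: from 0.15 + 0.85 × 0.265 × 0.2 × 0.08 = 0.1536 to 0.15 + 0.85 × 0.265 × 0.5 × 0.415 = 0.1967. The false-positive rate is 7.7% to 25%, with 0.1 to 1.9 credited patients expected per 40.
- d = 7.6%: p from 0.1510 to 0.1634. The false-positive rate is 7.0% to 10.6%, with at most 0.5 credited patients expected.

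Both formulas treat every adverse-event stop as occurring before progression and as unrelated to outcome on study drug.

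**The case against.** **This is silence, not a stated rule.** Nowhere does the plan say that scans after a switch count. Section 4.3 says only that assessments may continue, and Section 16.2 describes an independent response review committee whose handling of such scans is not given. That is fair, and a reader should not infer that the sponsor chose to count them. But the written definitions are complete without a new-therapy rule, and Section 12.4 says endpoints are derived programmatically. A programmer following them would include these scans.

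**The 6-month failure rule may already catch the PFS case.** Section 13.0 is headed as criteria for removal from study. If a switch ended follow-up before 6 months, the patient would be a failure under Section 14.0. This is arguable: the item sits in a list about giving no further study drug, and Appendix A keeps scanning until progression. A patient who switches and is still scanned is not clearly covered.

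**A reader might infer a known, large bias toward Arm 2 from 26.5% against 7.6%.** The documents do not support that. The rates come from different lung cancer studies. The 26.5% pools tremelimumab doses up to 10 mg/kg, and the cohort at the weight-based equivalent of this trial's dose (n = 11) had the fewest discontinuations for adverse events (Section 3.0). What stands is direction: Table 4 makes Grade 3 diarrhea or colitis a permanent stop on the combination but a hold on monotherapy.

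**Following PFS regardless of later therapy is a legitimate estimand.** So it is, and censoring at the switch may be informative. That argues for stating the choice, not for leaving it unstated.

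**Conclusion.** The point holds as a missing rule. No efficacy endpoint says what happens when a patient starts non-protocol systemic therapy before progression, and the definitions as written would credit that drug's effect to the arm.

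The firm sizes are those per credited patient: 9.8% to 19.6% for ORR (credited after stage 1) and 6.7% to 13.5% for 24-week PFS. The frequency is unknown. The upper figure of 25% for ORR needs three things together: the pooled 26.5% discontinuation, half of those patients switching before progression, and the highest response rate in the table. At the bottom of the range there is no inflation of ORR. Greater exposure of Arm 2 is plausible but cannot be sized. The sample size and decision boundaries need no change.

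**What to change.** In Sections 12.4 and 14.0:

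1. End the best-response window at the earlier of RECIST progression or the start of any non-protocol systemic anticancer therapy. Responses documented before the switch still count.
2. For the ≥10/40 rule, count a patient who starts such therapy before the 24-week assessment without documented progression as not progression-free. This matches the conservative failure rule already in Section 14.0.
3. For Kaplan-Meier PFS and duration of response, state one primary handling of new therapy and report the alternative as a sensitivity analysis. Censoring at the last assessment before the switch and counting the switch as an event are two candidates. Neither is free of assumptions.

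Cost: wording only. Appendix A already collects subsequent anticancer therapy at every follow-up time point; the sponsor should check that the start date is recorded. Sample size, boundaries and patient management are unchanged. The downside is that observed ORR and 24-week PFS may be slightly lower.

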Target Lesions	Non-Target Lesions	New Lesions	Overall Response	Best Overall Response when Confirmation is Required*
CR	CR	No	CR	≥4 wks. Confirmation**
CR	Non-CR/Non-PD	No	PR	≥4 wks. Confirmation**
CR	Not evaluated	No	PR	
PR	Non-CR/Non-PD/not evaluated	No	PR	
SD	Non-CR/Non-PD/not evaluated	No	SD	Documented at least once ≥4 wks. from baseline**
PD	Any	Yes or No	PD	no prior SD, PR or CR
Any	PD	Yes or No	PD	
Any	Any	Yes	PD	
* See RECIST 1.1 manuscript for further details on what is evidence of a new lesion. ** Only for non-randomized trials with response as primary endpoint. *** In exceptional circumstances, unequivocal progression in non-target lesions may be accepted as disease progression. **** . Note: Patients with a global deterioration of health status requiring discontinuation of treatment without objective evidence of disease progression at that time should be reported as “ symptomatic deterioration. ” Every effort should be made to document the objective progression even after discontinuation of treatment.				
*				

For Patients with Non-Measurable Disease (i.e., Non-Target Disease)

Date:

Non-Target Lesions	New Lesions	Overall Response
CR	No	CR
Non-CR/non-PD	No	Non-CR/non-PD*
Not all evaluated	No	not evaluated
Unequivocal PD	Yes or No	PD
Any	Yes	PD
* 'Non-CR/non-PD' is preferred over 'stable disease' for non-target disease since SD is increasingly used as an endpoint for assessment of efficacy in some trials so to assign this category when no lesions can be measured is not advised		

Duration of Response

Duration of overall response: The duration of overall response is measured from the time measurement criteria are met for CR or PR (whichever is first recorded) until the first date that recurrent or progressive disease is objectively documented (taking as reference for progressive disease the smallest measurements recorded since the treatment started). The duration of overall CR is measured from the time measurement criteria are first met for CR until the first date that progressive disease is objectively documented.

Duration of stable disease: Stable disease is measured from the start of the treatment until the criteria for progression are met, taking as reference the smallest measurements recorded since the treatment started, including the baseline measurements.

Progression-Free Survival

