14.0 BIOSTATISTICS

This Phase 2 study aims to assess the activity of Durvalumab alone and in combination with Tremelimumab in patients with recurrent or persistent endometrial carcinomas or endometrial carcinosarcomas. Patients will be randomized to Arm 1: Durvalumab (anti-PD-L1 Antibody) alone or Arm 2: Durvalumab with Tremelimumab (anti-CTLA-4 antibody). This is a randomized study however it is not powered to show superiority of one arm versus another.

In this study, all analyses will be performed by treatment arm.

To date, there are no published studies of immune checkpoint inhibitors in this patient population.

Extrapolating from prior monotherapy studies of immune checkpoint inhibitors in ovarian cancer have yielded overall response rates in the range of 10-15%, and may serve as a basis for historical comparison of the doublet tested here.

Study	N	ORR (CR+PR)	DCR (ORR+SD)	Prior Therapy
Nivolumab (anti-PD-1) 1 mg/kg q 2 weeks (cohort 1) 3 mg/kg q 2 weeks (cohort 2)	10 10	15% (3/20): 10% (1 PR) 20% (2 CR)	50% (5 SD +1 PR) 40% (2 SD +2 CR)	≥ 2 priors Platinum Resistant
Avelumab (anti-PD-L1) Phase Ib expansion cohort 10 mg/kg q 2 weeks	75	10.7% (8 PR)	55% (33 SD +8 PR)	med 4 priors(1-11) Platinum Resistant
Pembrolizumab (anti-PD-1) Phase Ib expansion cohort 10 mg/kg q 2 weeks	26	11.5% (1 CR, 2 PR)	35% (9 SD+1CR+2 PR)	>80% ≥ 4 priors PD-L1+ (IHC)

ORR (defined as CR+PR) will be the primary endpoint. A 10% ORR will be considered low and 25% or higher will be considered promising for further studies. Forty patients provide 90% power and Type I error of 10% using a Simon two stage minimax design. There will be an interim analysis after evaluable 27 patients and if 3 or more responders (CR+PR) are observed out of evaluable 27 patients then the study will continue to the second stage. At the end of the study we require 7 or more responders out of 40 patients to declare this study positive and the arm worthy for further investigation.

Unacceptable response rate: 0.1

Date:

Desirable response rate: 0.25
Error rates: Type I = 0.1 ; Type II = 0.1

# responses required in Stage I	# patients accrued at stage I	# responses required in Stage 2	Total sample size
≥ 3	27	≥ 7	40

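### Must Section 14 say whether the responders counted at 3/27 and 7/40 are confirmed or first-documented?

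*Combined protocol and SAP*

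**What the plan says.** Under the heading on best overall response, Section 12.4 states that the "best response assignment will depend on the achievement of both measurement and confirmation criteria". The table that follows, for patients with measurable disease, has a last column headed "Best Overall Response when Confirmation is Required" with an asterisk. Its CR and PR entries call for confirmation at four weeks or more and carry a double asterisk. The double-asterisk note reads: "Only for non-randomized trials with response as primary endpoint".

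Further on, under the permitted deviations from RECIST, Section 12.4 says that efficacy will be "evaluated according to the standard, unmodified RECIST v1.1 criteria described in section 12.3", and that "the efficacy analysis will be conducted by programmatically deriving each efficacy endpoint based on RECIST v 1.1 criteria".

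Section 14.0 applies the decision rules to each arm separately. At stage 1, "if 3 or more responders (CR+PR) are observed out of evaluable 27 patients then the study will continue to the second stage". At the end, "At the end of the study we require 7 or more responders out of 40 patients to declare this study positive". Neither sentence says confirmed or first-documented. Section 4.2 describes the study as randomized and open-label. Section 14.0 also calls it randomized, but adds that it is not powered to compare the arms.

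**The concern.** Read alone, the sentence on best overall response makes confirmation a requirement, while the footnote removes it for a randomized trial. Section 14.0 counts responders without choosing. Each arm is judged on a small integer, so one response can reverse the result at either look. The ORR result also decides whether the 24-week PFS rate is tested, and the higher ORR picks the winning arm if both arms pass, so the definition reaches beyond the single test.

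Two details add to the unease. The cross-reference for the RECIST criteria points to Section 12.3, which holds measurement methods, whereas the confirmation column is in Section 12.4. In addition, the stage 1 halt lasts 16 weeks from the last accrual and scans are eight-weekly. If treatment starts at accrual, a response first seen at week 16 in the last patient would have no scheduled confirming scan within the halt.

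**Working it through.** **Step 1: reproduce the design.** Inputs from Section 14.0: p0 = 0.10, p1 = 0.25, continue at 3 or more of 27, positive at 7 or more of 40.

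P(positive | p) = sum over x ≥ 3 of P(X1 = x; 27, p) × P(X2 ≥ 7 − x; 13, p).

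This gives 0.0977 at p = 0.10 and 0.9001 at p = 0.25. The stated 10% and 90% are reproduced, and a search for the minimax design returns the same sample sizes and cut-offs.

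**Step 2: read the passages together.** The general sentence says that confirmation criteria exist and matter. The table directly below it is where those criteria are given, in a column that applies when confirmation is required. The footnote says when that is: non-randomized trials with response as the primary endpoint. Response is a primary endpoint here, but patients are randomized (Sections 4.2, 14.0 and 15.3). The condition is not met, so CR or PR counts when measurement criteria are met. Dating duration of response from first documentation fits either reading, so it is not used as evidence.

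**Step 3: how much would the other reading change?** The documents give no rate of unconfirmed response, so f, the share of responders who fail confirmation, is an assumption. Confirmed responders then occur at rate p(1 − f). With one definition used at both looks, the chance of opposite final decisions for an arm is P(positive | p) − P(positive | p(1 − f)):

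| True ORR | f = 5% | f = 10% | f = 20% | f = 30% |
|---|---|---|---|---|
| 10% | 1.9% | 3.5% | 6.1% | 7.8% |
| 15% | 5.2% | 10.1% | 19.3% | 27.0% |
| 20% | 5.6% | 11.7% | 25.1% | 38.8% |
| 25% | 3.5% | 7.8% | 19.2% | 34.1% |
| Maximum over true ORR | 5.9% | 12.0% | 25.1% | 39.1% |

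The boundary case looks more dramatic. Given exactly 7 first-documented responders, the chance that fewer than 7 are confirmed is 1 − (1 − f)^7, or 30%, 52%, 79% and 92% for the four values of f. But an arm ends with exactly 7 of 40 only 5.6%, 14.7% and 8.3% of the time at true ORR 10%, 20% and 25%.

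**Step 4: does either definition protect the error rates?** Only if it matches the definition behind the 10% and 25% references, which Section 14.0 does not give.

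| Mismatch | f = 5% | f = 10% | f = 20% | f = 30% |
|---|---|---|---|---|
| References are any response, confirmed ones counted: power, P(positive \| 0.25(1 − f)) | 86.6% | 82.2% | 70.8% | 55.9% |
| References are confirmed, first-documented ones counted: type I error, P(positive \| 0.10/(1 − f)) | 12.0% | 14.7% | 22.4% | 33.9% |

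Each choice has its own cost. The documents do not show that confirmed response is the better calibrated count, nor that the first-documented count is sure to hold 9.8% and 90.0%.

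**Step 5: the halt.** Confirmation timing at week 16 matters only if confirmation is required. Under the reading in Step 2 no response waits for a second scan.

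**The case for a change.** The best opposing argument is that randomization does no work in the primary test. Each arm is compared with fixed rates, there is no powered comparison, and response is a primary endpoint. That is the kind of use for which the footnote reserves confirmation, so a programmer or response reviewer could defend requiring it. Section 3.0 also labels another study's response rate as including unconfirmed responses, so the authors know the distinction and left it off their own endpoint. And a clarifying sentence would be cheap.

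Part of this stands. The argument from purpose is reasonable, and the general sentence would read better if it were conditional. But the footnote turns on whether the trial is randomized, not on how the arms are tested, and this one is. Following the text therefore gives one rule, which can be applied at both looks.

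The other supports are weaker. The reference to Section 12.3 is a numbering slip: Section 14.0 makes the same slip for irRECIST, and Section 4.3 correctly points to 12.4 for its criteria. It creates no second definition. As for the open-label setting, Section 16.2 describes a committee for independent response review in trials with efficacy as a primary objective. That does not settle confirmation, but it bears on the worry about discretion.

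**Conclusion.** The concern does not call for a change. The wording is untidy, but the table and its footnote supply a usable rule: in this randomized trial a CR or PR counts when first documented. A sentence in Section 14.0 repeating this would restate the rule without altering the analysis. Moving to confirmed response would be a different choice with its own cost, and the documents give no basis for preferring it.

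The size depends wholly on an assumed failure rate. At 5% unconfirmed the readings disagree on an arm's final decision at most 5.9% of the time. The larger figures, up to 39.1%, need 30% unconfirmed and a true ORR near 21%, and the documents support neither value. The 9.8% and 90.0% hold if the reference rates and the count use the same definition. That is not stated, and writing down the counting rule would not by itself resolve it.
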